## Brief Summary of Research (250-400 words):

The investigational drug being studied in this protocol is Incobotulinumtoxin A (Xeomin®). Botulinum toxin (BoNT) prevents the release of the acetylcholine from peripheral nerves, inhibiting muscle contractions. BoNT is effective in relaxing overactive muscles. In musician's dystonia, the ability to reduce abnormally overactive muscles in the hand can be critical for the musical professional to continue his or her career. With the use of EMG/electrical stimulation and/or ultrasound guidance, the injector can precisely localize the individual muscles that are affected in this condition with great accuracy. Prior studies have shown that BoNT injections produce beneficial effects in forearm muscles, and less effect in shoulder or proximal arm muscles.

Possible risks in treating patients with BoNT include excessive weakness of the injected muscles. The drug may also affect non-targeted muscles. However these risks will be minimized during the screening period by carefully targeting the affected muscles and by administering low doses of BoNT. Small booster doses may be given at follow up visit (2, 4, 14 and 16-weeks after the primary injection date) if the initial injection was insufficient to produce sufficient efficacy in relief of the focal dystonia and did not produce excess weakness of the targeted muscle.

 Mount Sinai	Protocol Title:	A PLACEBO-CONTROLLED, DOUBLE-BLIND, RANDOMIZED, CROSS OVER PILOT STUDY OF THE EFFICACY AND TOLERABILITY OF INCOBOTULINUM TOXIN A (XEOMIN) AS A TREATMENT FOR FOCAL TASK-SPECIFIC DYSTONIA OF THE MUSICIAN'S HAND
	Principal Investigator Name/Contact Info:	[name].
	Primary Contact Name/Contact Info	[name] [contact]
	Date Revised:	10/22/2019
	Study Number:	HS: 13-00822 GCO: 13-1679

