## f) Procedures Involved in the Human Research

Every patient's dystonic movement disorder will be videotaped at each time point. The patient will bring in their instrument if possible; a keyboard will be provided for pianists. The patient will be encouraged to wear similar clothing/jewelry/nail polish etc. so each video recording will be identical at each time point.

The study will last a total of 24-28 weeks with the schedule as follows:

Visit 1- (Day 0) - Screening and baseline:

- Consent Form Process – completed prior to any research procedures
- Comprehensive Neurologic History and Physical Examination (MRC scales and dynamometry)
- Blood tests
- Patient's subjective rating scale of symptoms at baseline, HADS and perceived stress (questionnaires)
- Video of targeted hand(s) by [name] at NYU Langone medical center
- Selection of Muscles to inject – by [name] at NYU Langone medical center.
- Identification of the muscles and Injection of muscles

Visit 2 and Visit 3 will contain the following evaluations:

- Brief neurological exam to evaluate for weakness of the targeted muscles and surrounded non-targeted muscles (dynamometry, and MRC )
- Patient's subjective rating scale of symptoms, HADS and perceived stress (questionnaires)
- Assess for side effects
- Video of targeted hand(s) by [name] at NYU Langone medical center.
- Administer booster to patients who feel symptoms have not improved

Visit 4

 Mount Sinai	Protocol Title:	A PLACEBO-CONTROLLED, DOUBLE-BLIND, RANDOMIZED, CROSS OVER PILOT STUDY OF THE EFFICACY AND TOLERABILITY OF INCOBOTULINUM TOXIN A (XEOMIN) AS A TREATMENT FOR FOCAL TASK-SPECIFIC DYSTONIA OF THE MUSICIAN'S HAND
	Principal Investigator Name/Contact Info:	[name].
	Primary Contact Name/Contact Info	[name] [contact]
	Date Revised:	10/22/2019
	Study Number:	HS: 13-00822 GCO: 13-1679

- Brief neurological exam to evaluate for weakness of the targeted muscles and surrounded non-targeted muscles (dynamometry, MRC)
- Patient's subjective rating scale of symptoms, HADS and perceived stress (questionnaires)
- Assessment of side effects
- Video of targeted hand(s) Injection of muscles by [name] at NYU Langone medical center.

Visit 4a or 4b. This is optional visit at Week 6, 8 are depending on optimal dosing at weeks 2 and 4.

This visit will assess the improvement in musical performance. It will be 4 weeks after optimal booster injection.

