- Brief neurological exam to evaluate for weakness of the targeted muscles and surrounded non-targeted muscles (dynamometry, and MRC )
- Patient's subjective rating scale of symptoms and perceived stress (questionnaires)
- Assess for side effects
- Video of targeted hand(s) by [name] at NYU Langone medical center.

Visit 5; Week 12 (week 14 or 16 depending on previous dosing schedule) will contain the following evaluations:

- Brief neurological exam to evaluate for weakness of the targeted muscles and surrounded non-targeted muscles (dynamometry, and MRC )
- Patient's subjective rating scale of symptoms, HADS and perceived stress (questionnaires)
- Assess for side effects
- Video of targeted hand(s) (Groups 1 & 2 will be crossed over and will receive their 2nd injection cycle) by [name] at NYU Langone medical center.
- Treatment may be deferred for up to 2-4 weeks in any individuals who have persistent weakness from the first treatment cycle

 Mount Sinai	Protocol Title:	A PLACEBO-CONTROLLED, DOUBLE-BLIND, RANDOMIZED, CROSS OVER PILOT STUDY OF THE EFFICACY AND TOLERABILITY OF INCOBOTULINUM TOXIN A (XEOMIN) AS A TREATMENT FOR FOCAL TASK-SPECIFIC DYSTONIA OF THE MUSICIAN'S HAND
	Principal Investigator Name/Contact Info:	[name].
	Primary Contact Name/Contact Info	[name] [contact]
	Date Revised:	10/22/2019
	Study Number:	HS: 13-00822 GCO: 13-1679

Visit 6 and visit 7; Week 14 or 16 or 18 depending on previous dosing schedule will contain the following evaluations:

- Brief neurological exam to evaluate for weakness of the targeted muscles and surrounded non-targeted muscles (dynamometry, and MRC )
- Patient's subjective rating scale of symptoms, HADS and perceived stress (questionnaires)
- Assess for side effects
- Video of targeted hand(s) by [name] at NYU Langone medical center
- Administer booster to patients who feel symptoms have not improved

Visit 7a or 7b is optional visit which will be 4 week after optimal dosing injection.

- Brief neurological exam to evaluate for weakness of the targeted muscles and surrounded non-targeted muscles (dynamometry, and MRC )
- Patient's subjective rating scale of symptoms, HADS and perceived stress (questionnaires)
- Assess for side effects
- Video of targeted hand(s) by [name] at NYU Langone medical center

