## **MSSM Co-Principal Monitor:**

Last Name: [name]  
Academic Title: Professor  
Department: Neurology  
Mailing Address: [name]  
[name]  
E-mail: [contact]

First Name: [name]  
[contact]  
[contact]

Drs. [name] and [name] have extensive experience in the area of movement disorders. [name] is an expert in the use of toxin's in the treatment of dystonia and [name] is highly knowledgeable about the musicians who have been diagnosed with dystonia as it relates to playing his or her musical instrument. Their extensive knowledge will ensure patient safety throughout the study.

- 1) Adverse events (AE) will be monitored for safety. At each visit subjects will be asked non-leading questions such as “do you feel different in any way since the last visit?” All observed or volunteered AE’s will be documented in the AE log.
- 2) Accumulated safety and data information will be reviewed by the monitors ([name] and [name]) during study team meetings.
- 3) The study does not require any stopping rules for interrupting the study or altering the study design. The treatments used for the study are lower doses than standard of care.
- 4) Incobotulinumtoxin A is being used on average doses between 10U and 30 Units per subject, but at no time will any subject receive over 100 Units. Each study visit, the assessing physician will select the muscles and the amounts of medication to be injected. The selection sheet will be provided to the unblinded co-investigator to preparing the syringes either with placebo or study drug.
- 5) AEs will be classified as mild, moderate or severe based upon the following criteria: Mild = symptoms do not alter the subject’s normal functioning, Moderate= symptoms produced some degree of impairment to function but are not dangerous, uncomfortable or embarrassing to the subject, Severe =

 Mount Sinai	Protocol Title:	A PLACEBO-CONTROLLED, DOUBLE-BLIND, RANDOMIZED, CROSS OVER PILOT STUDY OF THE EFFICACY AND TOLERABILITY OF INCOBOTULINUM TOXIN A (XEOMIN) AS A TREATMENT FOR FOCAL TASK-SPECIFIC DYSTONIA OF THE MUSICIAN'S HAND
	Principal Investigator Name/Contact Info:	[name].
	Primary Contact Name/Contact Info	[name] [contact]
	Date Revised:	10/22/2019
	Study Number:	HS: 13-00822 GCO: 13-1679

symptoms are dangerous to the subject's well-being and causes significant impairment of function or incapacitation.

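### The booster condition in the summary conflicts with the one in the visit lists, and neither says how the non-targeted-muscle exam enters the decision

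*Combined protocol and SAP*

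**What the plan says.** **Brief Summary of Research.** Small boosters are permitted "2, 4, 14 and 16-weeks after the primary injection date", subject to two conditions: "if the initial injection was insufficient to produce sufficient efficacy in relief of the focal dystonia", and the injection "did not produce excess weakness of the targeted muscle". The same paragraph warns: "The drug may also affect non-targeted muscles".

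**Section 5(f), Visits 2 and 3, and Visits 6 and 7.** Both lists require "Brief neurological exam to evaluate for weakness of the targeted muscles and surrounded non-targeted muscles", by dynamometry and MRC scale. Both end with the instruction "Administer booster to patients who feel symptoms have not improved". No weakness condition is attached, for any muscle.

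**Section 5(f), Visit 5 (crossover).** "Treatment may be deferred for up to 2-4 weeks in any individuals who have persistent weakness from the first treatment cycle". The weakness is not limited to the targeted muscle.

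**Section 5(i), item 4 of the monitoring list.** "Each study visit, the assessing physician will select the muscles and the amounts of medication to be injected". Section 19 adds that at treatment visits the blinded investigator assesses the patient and then enters muscles and amounts on the injection form. Neither section gives a criterion for withholding a booster.

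**The concern.** Boosters are extra doses of the product under test, so the rule for who receives one is part of the treatment being compared. Here the rule depends on which section the staff follow. The summary is permissive and carries a weakness limit. The visit lists, which staff would work from on the day, are worded as an instruction, rest on the patient's own impression, and carry no weakness limit.

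There is also a gap that both versions share. The protocol names effects on non-targeted muscles as a risk and tests those muscles at every booster visit, but it does not say what the result means for the booster.

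Two things are at stake. One is safety: the supplied text contains one weakness limit on boosters, in the summary, and the visit lists do not repeat it. The other is consistency of the regimen. Musical performance is the primary outcome, muscle weakness is a secondary outcome, and the optional Visit 4a/4b assesses performance four weeks after the optimal booster. If different patients are boosted under different conditions, the efficacy and tolerability results describe a regimen that cannot be stated exactly.

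**Working it through.** The plan gives no figure on this point, so the main check sets the passages side by side.

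**Step 1. Apply each version literally to a patient who feels unimproved and whose relief was insufficient.**

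| Exam finding at the booster visit | Summary | Visit 2/3 and 6/7 lists | Result |
|---|---|---|---|
| No weakness | Booster permitted | Booster to be given | Compatible |
| Excess weakness of the targeted muscle | Booster not permitted | Booster to be given | Direct conflict |
| Weakness of a non-targeted muscle only | Booster permitted; finding not mentioned | Booster to be given; finding not mentioned | No written use of the finding |

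The second row is the contradiction. The third row is the gap.

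**Step 2. Compare with the crossover visit.** The Visit 5 deferral rests on persistent weakness of any muscle. The protocol therefore treats weakness in three ways: targeted muscle only (summary), not at all (booster lines of the visit lists), and without restriction (Visit 5).

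**Step 3. Number of decisions affected.** The summary gives four booster times, so 20 patients × 4 = 80 booster decisions. Half of them, 40, fall in BoNT cycles if every patient completes both cycles.

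**Step 4. Upper bound for the third row.** The documents give no rate of non-targeted weakness. Let p be an assumed probability per BoNT cycle, with one such cycle per patient and independent patients. The chance that at least one of 20 patients has non-targeted weakness is 1 − (1 − p)^20, and the expected number is 20p.

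- p = 0.05: 1 − 0.95^20 = 0.64; expected 1
- p = 0.10: 1 − 0.90^20 = 0.88; expected 2
- p = 0.20: 1 − 0.80^20 = 0.99; expected 4

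These are upper bounds at each p, because the third row also requires insufficient relief and no excess weakness of the targeted muscle. If those further conditions held in a share q of such cycles, p is replaced by pq. With q = 0.25, also an assumption:

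- pq = 0.0125: 1 − 0.9875^20 = 0.22; expected 0.25
- pq = 0.025: 1 − 0.975^20 = 0.40; expected 0.5
- pq = 0.05: 1 − 0.95^20 = 0.64; expected 1

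The spread, from 22% to 99%, reflects the assumptions and not the trial. None of these figures applies to the second row, for which the documents give no rate either.

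**The case against.** The strongest reply is that clinical judgement closes the gap. The summary only permits boosters. The assessing physician selects muscles and amounts at each visit, and the visit lists put the exam before the booster. This stands against a stronger reading that a reader might infer: that weakness of a non-targeted muscle does not stop a further dose, or that the exam result plays no part in any booster decision. The documents do not support that. They show that no written criterion exists, not that the finding is ignored.

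A second reply is that Visit 5 does not contradict the booster rule. This also stands. The deferral is itself optional, names no muscle group, and concerns the start of a new treatment cycle, not a small booster. It shows that weakness is described differently in different places, and no more.

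A third reply is that strength testing has its own purpose, since Section 5(e) lists it as a secondary outcome to document weakness. That is correct: testing a muscle does not oblige the protocol to make it a dosing criterion. But the protocol did choose to write a weakness limit, and leaves unclear how far it extends.

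A reader might also infer that boosters in such patients lower performance in the BoNT cycle and so distort the estimated effect. The documents do not say that weakness from spread impairs playing. Weakness after a booster is also part of the tested regimen's effect and is measured at the follow-up visits. No direction of bias can be claimed.

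Finally, the low doses and the 100-unit ceiling in Section 5(i) limit the likely harm. They do not remove the conflict between the two statements of the rule.

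**Conclusion.** The point holds as a conflict and a gap in the written booster condition. Followed literally, the visit lists give a booster to a patient with excess weakness of the targeted muscle, whom the summary excludes. Neither version states how weakness of a non-targeted muscle is to be used. Both conclusions rest on the wording alone and need no assumption about rates.

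How often either situation arises cannot be estimated from the documents. The 64%, 88% and 99% are ceilings for the non-targeted case at assumed rates, not expected frequencies. Discretion may prevent a booster in these patients, so the finding is a missing and inconsistent criterion, not a demonstrated harm. It should be corrected because it governs an extra dose and the correction is cheap.

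**What to change.** The Brief Summary of Research and Section 5(f) (Visits 2/3, 5 and 6/7) must be reconciled. Write one booster condition and use it word for word in the summary and in both booster visit lists. It should state:

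- whether a weakness condition applies at the booster visits;
- how the results for the targeted muscles and for the non-targeted muscles at that visit each enter the decision;
- whether the patient's impression, the examiner's judgement or both establish insufficient relief.

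The content of the clinical rule is for the investigators to set; this review does not propose one. The Visit 5 wording should be read against the new text so that the term weakness is used knowingly in each place, whether or not the rules are meant to match.

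The cost is amendment wording. No new test or visit is needed, because the exam is already done at each booster visit. The injection form is not among the documents, so whether it already shows the exam result should be checked at the same time.

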## 1) Objectives:

The research question of this exploratory crossover pilot trial is: compared to placebo, does BoNT significantly improve the motor performance and subjective disability of patients suffering from focal task specific dystonia of the musician's hand? Focal task-specific dystonia of the musician's hand is a disorder that frequently impairs or ends the careers of highly skilled performing artists. [name] has personally evaluated more than 170 of these patients over the last decade; clinically and anecdotally, BoNT is often used to treat these musicians, but few studies exist that quantify their motor and subjective improvement or the prevalence of adverse effects. This trial will be performed using BoNT versus placebo in 20 patients with musician's hand dystonia, to refine quantitative measures of performance using Musical Instrument Digital Interface (MIDI) technology and high speed video analysis, demonstrate efficacy and tolerability of BoNT injections, and provide power calculations for a future multi-center double blind clinical trial.

## 2) Background

Musician's dystonia (MD) is characterized by sustained muscle contractions and the loss of voluntary muscle control; this leads to incoordination and an inability to properly play one's musical instrument. The condition is almost exclusively triggered by the act of playing music, and is therefore considered to be a type of focal task-specific dystonia. (1,2,12,13) The dystonia can involve muscles of the hand, limb, or embouchure.(1,4) MD typically affects highly trained musicians and is often disabling; it affects up to 1% of professional musicians. (3)

The pathophysiology of musician's dystonia is not well understood. A commonly accepted theory suggests deregulation of normal mechanisms of brain plasticity. Changes in brain plasticity have been demonstrated in string players where the sensory-motor cortical receptive fields of the fingers enlarge with repetitive tasks.(5) As these new cortical projections are created, they not only have the potential to augment fine motor control of individual fingers, but may also be susceptible to disorganization which may lead to dystonia. (6,7) Genetic predisposition is also thought to be a factor in the development of MD. In one study, up to 10% of patients with MD were found to have at least one family

 Mount Sinai	Protocol Title:	A PLACEBO-CONTROLLED, DOUBLE-BLIND, RANDOMIZED, CROSS OVER PILOT STUDY OF THE EFFICACY AND TOLERABILITY OF INCOBOTULINUM TOXIN A (XEOMIN) AS A TREATMENT FOR FOCAL TASK-SPECIFIC DYSTONIA OF THE MUSICIAN'S HAND
	Principal Investigator Name/Contact Info:	[name].
	Primary Contact Name/Contact Info	[name] [contact]
	Date Revised:	10/22/2019
	Study Number:	HS: 13-00822 GCO: 13-1679

member with dystonia. (3) This familial relationship was noted to be much higher in another study after a thorough history and clinical exam was conducted amongst musicians with dystonia as well as their family members. (8) No specific candidate gene has been identified to date.

Risk factors that are thought to be contributory to the development of MD have been observed in a German study of 591 patients with MD. These included prolonged hours of practice, movements that required a high level of spatial and temporal precision as well as a predefined temporo-spatial constraints, chronic pain, anxiety and perfectionism. In addition, males appeared to be slightly more affected than females. (7)

Treatment of musician's dystonia is often challenging as the pathophysiology of the condition is not well understood, and there are often high expectations for a curative measure by the patient. Available treatment options include both pharmacologic and non-pharmacologic treatments. Non-pharmacologic treatment consists of rehabilitation techniques that practice tactile discrimination with the hope that sensory retraining could alleviate the motor symptoms of MD. Ergonomic changes to the musical instrument have also been tried to help alleviate motor symptoms. Pharmacologic treatment consists of oral medications such as trihexyphenidyl, baclofen, phenytoin and primadone, and injections with botulinum toxin. (9) Unfortunately, with the exception of botulinum toxin injections, most treatment options have shown suboptimal results.

BoNT injections have shown mixed results in treating focal dystonia, including focal task specific dystonia.(11) The toxin can chemically denervate the overactive muscle by blocking the transmission of nerve impulses that innervate the dystonic muscle. With EMG/electrical stimulation guidance, the muscles contributing to the movement disorder can be targeted with fine precision. More recently ultrasound has been employed effectively in muscle targeting. BoNT therapy works best for forearm muscles and does not show great effect in treating embouchure's dystonia or dystonia affecting shoulder or proximal arm muscles. (2,9) In one study that treated 84 patients with MD with injections of botulinum toxin, 58% of musicians experienced improvement of symptoms and 36% experienced long term benefit in their performance ability. (10)

 Mount Sinai	Protocol Title:	A PLACEBO-CONTROLLED, DOUBLE-BLIND, RANDOMIZED, CROSS OVER PILOT STUDY OF THE EFFICACY AND TOLERABILITY OF INCOBOTULINUM TOXIN A (XEOMIN) AS A TREATMENT FOR FOCAL TASK-SPECIFIC DYSTONIA OF THE MUSICIAN'S HAND
	Principal Investigator Name/Contact Info:	[name].
	Primary Contact Name/Contact Info	[name] [contact]
	Date Revised:	10/22/2019
	Study Number:	HS: 13-00822 GCO: 13-1679

Musician's dystonia is a highly disabling disorder and can be a devastating condition to the professional musician. Although there is no cure that is currently available, treatment with BoNT can offer great symptomatic relief which may enable the musician to continue their ability to perform.

### **4) Resources Available to Conduct the Human Research**

Drs. [name] and. [name] are experts in the treatment of focal dystonia. They have many patients that fit the inclusion criteria of musician's dystonia. Many of the patients will be referred from [name] practice at NYU Langone Medical Center due in part to his connections with musicians from the Julliard School and other music schools, organizations, and support groups. A total enrollment of 20 patients is anticipated over the course of the study.

The study team meets monthly to discuss the research projects which are enrolling and the various stages of recruitment and to troubleshoot any issues which arise. Additionally the study team will be educated about the protocol, the investigational product, and their trial-related duties and functions, through these study team meetings. More frequent meetings will be added should a delay in enrollment occur or if there are major issues concerning the flow of subjects through the visits of the study.

Drs. [name]'s, [name]'s and [name]'s qualifications are included in this application which includes their biosketches. Their required research education and conflict of interest statements are available for review

